Exclusion criteria are parent(s) who (a) has (have) severe mental illness that would interfere with their ability to participate in PT (measured by the Psychosis Subscale of the Basic-24 or diagnostic intake clinician assessment) and/or (b) is (are) actively using drugs or alcohol, based on clinician assessment at intake. Foster parents or relatives without legal status for the child are excluded since they may not be able to complete the study.. Children who are actively suicidal, psychotic, or who have significant developmental delay (i.e., fail developmental screening using Ages and Stages Questionnaire at intake), congenital, genetic, or sensory abnormalities that interfere with the child’s understanding, cooperation, and/or participation in PCIT or CPP will be excluded and referred for appropriate treatment services or hospitalization. Children diagnosed with autism or Pervasive Developmental Disorder will also be excluded since there is no evidence that CPP or PCIT is effective with these populations.

6. Drugs/ Substances/ Devices

- a. NA
- b. NA.
- c. NA

7. Study Statistics

- a. Primary outcome variables: Child behavior problems (parent report and observed from video recorded parent-child play/clean-up), parenting self-efficacy, parent discipline, parent behavior (observed from video recorded play/clean-up), parent satisfaction, parent engagement in the intervention, parent attendance in PT sessions.
- b. Secondary outcome variables: cost variables are those related to (1) time required to administer PT (including lost time for missed appointments) and additional non-PT therapy services used by parent or child (i.e., individual therapy, medications); (2) therapist time, (3) parent time, (4) childcare provided during CPP sessions; (5) space (including one-way mirror).
- c. Sample Size and Statistical Plan: Sample size in this equivalence study is designed to determine whether CPP is as effective as PCIT for the targeted clinical population (i.e., outcomes do not differ clinically or statistically). We used CBCL scores (child behavior problems) to estimate the sample size positing the null hypothesis that the absolute difference in the post intervention means between the CPP and PCIT groups will be > 0.5 standard deviations (i.e., > 5 point difference on the CBCL). The alternative hypothesis is that the absolute difference in the two means is less than or equal to 0.5

Date: January 30, 2012
Principal Investigator: [name]

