Application Number: NA_00039328

standard deviations. We will use the more conservative two-sided test. Thus, with 300 participants (150/condition) we will have 99% power to detect this difference using a two-sample comparison of means with alpha=0.05.

Hypothesis testing will mainly be conducted using repeated-measures MANOVA. Should the MANOVA be significant, univariate ANOVA will follow to identify the source of those differences. MANOVA was determined to be a more desirable approach than random regression models because MANOVA corrects for multiple tests of hypotheses. All baseline difference analyses and hypothesis testing will be conducted using 2-tailed tests and alpha =.05 (except tests to examine baseline differences between conditions, which will use .01 to correct for the multiple tests of hypotheses).

d. Early stoppage rules. Interventions will be discontinued if (a) more than 50% of parent participants in either condition report dissatisfaction on consumer satisfaction surveys with their assigned intervention or (b) more than 50% of child participants' CBCL scores (in either condition) worsen from baseline by $> .5$ SD. In this event, the research team will immediately convene with the members of the DSM committee to carefully review the protocol, reasons for dissatisfaction, and recommendations for change. A data safety and monitoring committee will meet early in the first year of the study to make additional recommendations for stoppage rules.

8. Risks

- a. Medical risks. Parent-Child Interaction Therapy and the Chicago Parent Program are psychosocial parent training interventions that have shown no evidence of medical risk. The major risks of this study are disclosure of confidential information and discomfort with the personal nature of some of the survey questions. These risks are no greater than what parents would be exposed to in a mental health treatment setting.
- b. Efforts to minimize risk. Efforts have been taken to minimize risk through appropriate training of research and clinical staff and the use of random number subject identifiers. All therapists have licensed and experienced therapists and have completed the appropriate training (PCIT or CPP).

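### The baseline score is collected for the child-behaviour and parenting outcomes but not named as a covariate; adjusting for it would sharpen the CPP–PCIT comparison at no cost

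*Combined protocol and SAP*

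**What the plan says.** Section 7c sets the hypothesis on the "absolute difference in the post intervention means between the CPP and PCIT groups", with a null that the "CPP and PCIT groups will be > 0.5 standard deviations (i.e., > 5 point difference on the CBCL" scale. Power is stated for an unadjusted comparison at 150 per condition, two-sided: "we will have 99% power to detect this difference using a two-sample comparison of means with alpha=0.05".

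The analysis sentence reads "Hypothesis testing will mainly be conducted using repeated-measures MANOVA", with univariate ANOVA to follow if the MANOVA is significant. It does not say whether T1 is one of the repeated measures, or whether the group effect or the group-by-time effect answers the question.

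Table 1 (Section 4b) lists CBCL, DPICS (child and parent behaviour), TCQ and PQ at T1, T2 and T3. The only covariates named for the analyses are additional therapies received during the study (Section 4a). For baseline differences between conditions, Section 7c offers only significance tests at the .01 level.

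**The concern.** In a randomised trial, the baseline value of the outcome is usually the strongest available predictor of its follow-up value. Conditioning on it removes explained variance and corrects the linear effect of chance baseline imbalance. This matters particularly for an equivalence question, where the estimate has to be precise enough to exclude differences beyond the margin in both directions.

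On the plan's wording, the T1 score could go unused (post-intervention means only, or MANOVA on T2 and T3). It could enter as an unconstrained response, so that the group-by-time comparison is in effect a comparison of change. Or it could be averaged into a group main effect, which dilutes the comparison with a time point that precedes treatment. None of these is as precise as using T1 as a covariate. Meanwhile the covariates that are named arise after randomisation.

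**Working it through.** **Inputs.** From Section 7c: 150 per arm; two-sided alpha 0.05; margin 5 points = 0.5 SD, so SD = 5/0.5 = 10. The correlation r between baseline and follow-up CBCL is not in the documents; r = 0.3, 0.5 and 0.7 are assumed (0.6 is added for the sample-size ratios). The formulas also assume equal SD at T1 and follow-up, one follow-up time, complete data and independent families.

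**The plan's own figure.** SE = 10 × √(2/150) = 1.155. Power = Φ(5/1.155 − 1.960) = Φ(4.330 − 1.960) = Φ(2.370) = 0.991. The stated 99% is reproduced.

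**Precision.** The effective SD is 10 for raw post means, 10√(2(1 − r)) for a change contrast and 10√(1 − r²) for ANCOVA. The 95% half-width is 1.96 × SD × √(2/150). For example, ANCOVA at r = 0.5 has SD 10√0.75 = 8.66, SE 1.00 and half-width 1.96.

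| r (assumed) | Raw post means | Change contrast | ANCOVA |
|---|---|---|---|
| 0.3 | 2.26 | 2.68 | 2.16 |
| 0.5 | 2.26 | 2.26 | 1.96 |
| 0.7 | 2.26 | 1.75 | 1.62 |

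These are CBCL points. A simulation of 4,000 trials at each r gave matching standard errors (at r = 0.5: 1.14, 1.16 and 1.00, against 1.155, 1.155 and 1.00 by formula).

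**Equivalent sample size.** This is the ratio of variances.
- Raw post means against ANCOVA: 1/(1 − r²) = 1.33, 1.56, 1.96 at r = 0.5, 0.6, 0.7, that is 33%, 56% and 96% more participants.
- Change contrast against ANCOVA: 2/(1 + r) = 1.33, 1.25, 1.18, that is 33%, 25% and 18% more.

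The two gains run in opposite directions as r rises, so neither series should be quoted alone.

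**Equivalence power.** The plan gives no equivalence decision rule. As an assumption, take equivalence to be shown when the 95% CI lies inside ±5. For true difference δ, power = Φ((5 − δ)/SE − 1.96) − Φ((−5 − δ)/SE + 1.96). For example, ANCOVA at r = 0.5 and δ = 2 gives Φ(3/1.00 − 1.96) = Φ(1.04) = 0.851.

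| | δ = 0 | δ = 2 points |
|---|---|---|
| Raw post means | 0.982 | 0.738 |
| Change, r = 0.3 / 0.5 / 0.7 | 0.911 / 0.982 / >0.999 | 0.592 / 0.738 / 0.918 |
| ANCOVA, r = 0.3 / 0.5 / 0.7 | 0.990 / 0.998 / >0.999 | 0.777 / 0.851 / 0.953 |

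**Sensitivity to loss.** The plan gives no dropout rate. Section 3 cites 36% early termination from PCIT in another study. If both arms lost that share (an assumption), 150 × 0.64 = 96 per arm remain. Power at δ = 0 is then 0.868 for raw post means and 0.905, 0.959 or 0.996 for ANCOVA at r = 0.3, 0.5, 0.7.

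**Chance imbalance.** A baseline test at .01 does not flag a difference below 2.576 × 1.155 = 2.97, about 3 points. At r = 0.5, a 3-point imbalance shifts raw post means by 0.5 × 3 = 1.5 points, and change scores by (1 − 0.5) × 3 = 1.5 points the other way. That is the extreme; a one-SE imbalance is 1.15 points, with a shift of about 0.6. ANCOVA removes the linear part.

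**The case against.** The strongest reply is that little is lost at the design point. The unadjusted half-width of 2.26 is under half the 5-point margin, and at full enrolment with zero true difference adjustment adds less than 2 percentage points of power. Sizing on unadjusted means is also a common simplification, and is conservative if the analysis later uses baseline. All of this stands.

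Nor does the plan ignore baseline. Objective 4 describes effect size as improvement from baseline, and the exploratory aim examines effects by baseline severity. If T1 is among the repeated measures, baseline already enters through change. A repeated-measures model with baseline means constrained equal across arms can match ANCOVA. These points limit the size of the gain, but none specifies baseline adjustment of the main comparison.

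Three stronger readings are tempting and are not supported:
- A reader might infer that the 99% power is wrong. It reproduces.
- A reader might infer that the plan commits to raw post means, or to a time-by-group test. The first is the wording of the hypothesis and power statement; the second is not in the text. The role of T1 is simply unspecified.
- A reader might infer that the choice widens the interval that decides equivalence. The plan specifies no confidence interval or pair of one-sided tests for that decision. Pairing an equivalence null with a MANOVA difference test is a separate and larger gap.

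**Conclusion.** The point holds as one of efficiency and clarity; it does not invalidate the design. For any r strictly between 0 and 1, using T1 as a covariate is more precise than raw post means and than an unconstrained change contrast. The benefit is negligible for equivalence power at full N and zero true difference. It is material when the true difference is non-zero but inside the margin (11 percentage points over raw post means at δ = 2 and r = 0.5: 0.851 − 0.738), or when families are lost.

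The size rests on an assumed r, on SD 10 as implied by the margin, and on a 95% CI rule that the plan does not state. With a 90% CI instead, power at δ = 2 would go from 0.830 to 0.860, 0.912 or 0.977 at r = 0.3, 0.5, 0.7. Except in the 96-per-arm case, the figures are before dropout, and none allows for clustering within CPP parent groups.

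**What to change.** In Section 7c, state that the CPP–PCIT difference at follow-up in each outcome measured at T1, T2 and T3 is estimated from a linear model, or a likelihood-based longitudinal model, with the T1 value of the same measure as covariate (or with baseline means constrained equal across arms). For CBCL, state that the confidence interval of the adjusted difference is compared with the ±5-point margin, and give its level. Say which follow-up time the comparison refers to.

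This is a free improvement: wording only, with no added assessments or participants, because the T1 data are already scheduled. It should be fixed before outcomes are compared by arm.

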Using a randomized experimental design, 300 parents of 2-5 year old children (predominantly African American and economically disadvantaged) referred for behavior problems to the Family Center at Kennedy-Krieger Institute will be randomized to Parent-Child Interaction Therapy (PCIT; n=150) or Chicago Parent Program (CPP; n=150). Data on child behavior problems, parent discipline strategies, parenting self-efficacy, observed parent behavior, parent stress, and depression will be obtained from all participants at baseline and post-intervention assessments. Social risk will be assessed at intake. Parent satisfaction, attendance, and engagement in the intervention will be obtained at post-intervention. Clinical costs related to PT and non-PT treatment will be measured monthly. This innovative study will be the first to compare the effectiveness, cost, and social validity of a brief treatment designed with and for ethnic minority parents of young children against a well-established treatment considered to be the "gold standard." Determining whether a PT treatment can yield comparable effects for low-income, racial/ethnic minority parents of young children but at less cost, in less time, and with greater social validity is of significant public health importance.

2. Objectives: To compare the:

1. Effectiveness of PCIT and CPP for reducing behavior problems in a predominantly African American sample of children 2-5 years old from low-income communities. It is hypothesized that CPP will be equally as effective as PCIT for reducing child behavior problems based on parent report and observation.
2. Effectiveness of PCIT and CPP for improving parenting behavior and self-efficacy among a predominantly African American sample of parents of 2-5 year old children from low-income communities. It is hypothesized that CPP will be equally as effective as PCIT for improving parent discipline, self-efficacy, and observed parenting behavior.
3. Perceived social validity of PCIT and CPP based on parent satisfaction scores, treatment attendance, and parent engagement ratings (i.e., active parent participation in the intervention

Date: January 30, 2012
Principal Investigator: [name]
Application Number: NA_00039328

sessions). It is hypothesized that parents in the CPP condition will (a) attend a higher percent of PT sessions, (b) be more engaged, and (c) report higher satisfaction than parents in PCIT.

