- a. Design: This equivalence study will use an experimental design with randomization of parents seeking behavioral treatment for their 2-5 year old children at the Family Center (FC) in [name]. Equivalence studies are used to determine whether a novel treatment or health delivery model, that might be less costly or more acceptable to the treatment population, is at least as effective as another more well-established treatment. It is important to note that the participants in this study, who experience multiple adversities associated with urban poverty and mental health problems, may require more therapeutic services than just PT. As a result, parents and children may receive additional treatment (e.g., individual therapy, medication) other than PT. However, PT treatment (PCIT or CPP) will be randomly assigned and all additional therapies provided to the participating parent or child at the Family Center or other agencies during the course of this study (type, amount, and cost) will be accounted for in the study and included as co-variates in the analyses. In addition, the effect of parent depression and stress on PT outcomes will be evaluated. The strengths of this design include (a) the ability to determine whether families exposed to one PT program need more additional treatment than families exposed to the other PT program, (b) the ability to estimate the costs of additional therapy, (c)

Date: _ January 30, 2012 _____
 Principal Investigator: _ [name] _____
 Application Number: _ NA_00039328 _____

greater buy-in from clinicians who may be concerned that randomization will negatively affect treatment outcomes for their families, and (d) enhanced external validity of the study.

This study will use a block randomization procedure to facilitate the initiation of parent groups without lengthy waiting periods. Each block will consist of the next 19 eligible parents (estimated recruitment time=3-4 months). Following intake assessment by a FC clinician to determine study eligibility, parents who meet the inclusion criteria will be invited to participate in the study. Parents who state interest in participating and agree to have their name given to the Project Director will meet individually with the Project Director (to be hired) who will describe the study and obtain informed consent. Documentation of parent's agreement to be contacted by the Project Director will be placed in the child's medical record.

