b. Study duration and visits: Following consent, parents will be assigned to the appropriate block consisting of the next CPP group or the next available PCIT therapist. Participating parents and children will complete three assessment phases: baseline, 4 months post-baseline, and 9 months post-baseline. Each assessment phase includes parent-report surveys on child behavior problems, parenting self-efficacy, parent discipline strategies, stress, depressive symptoms, and attachment, and a 15- minute videotaped parent-child free play interaction (Dyadic Parent-Child Interaction Coding Systems; DPICS), followed by a clean-up session. Videotaped DPICS assessments will be coded by research colleagues at the University of Iowa ([name].) A Data Use Agreement will be obtained between Drs. [name], University of Iowa and [name], Johns Hopkins School of Nursing. Assessments typically require 45-75 minutes at each phase. All measures are described in Table 1 below.

Table 1. Parent-Child Variables, Measures, Informant, Items, Assessment Time-points*, Reliability, Validity

Variables	Measure(s)	Informant	# of Items	When Assessed	Reliability	Validity Evidence
Child Behavior Problems (parent)	Child Behavior Checklist (CBCL/1½-5) (Externalizing Scale & Internalizing Scale)	Parent	99	T1, T2, T3	.86-.89	[40; 41]
Child Behavior Problems (observed)	Dyadic Parent-Child Interaction Coding System (DPICS) (non-compliance, destructives, physical negatives, smart talk, cry, whine, yell)	Observer	7	T1, T2, T3	.73	[22; 57; 58]
Parent Self-Efficacy	Toddler Care Questionnaire (TCQ)	Parent	38	T1, T2, T3	>.93	[22; 57; 59; 60]
Parent Discipline	Parenting Questionnaire (PQ) (Warmth, Following Through, Corporal Punishment subscales)	Parent	50	T1, T2, T3	.68-.84	[22; 61]
Parent Depression	Center for Epidemiologic Studies Depression Scale-Revised	Parent	20	T1, T2, T3	>.85	
Parent Attachment	Attachment Style Questionnaire	Parent	40	T1	Test-retest .75-.80	
Parent Behavior	DPICS (Praise, Commands, Physical Coerciveness, Critical Statements, Positive/ Negative Affect)	Observer	10	T1, T2, T3	.88-.90	[22; 57; 58]
Social Validity: parent satisfaction w/ PT	Parent Satisfaction at end of program	Parent	4-12	T2 -CPP T3-PCIT	NA (items analyzed separately)	[34; 55; 57]
Social Validity: Degree to which parent actively participated in PT	Parent Engagement Scale	Clinician	7	T2-CPP T3-PCIT	.87	[35]

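### The protocol posits a ±5-point CBCL equivalence null but never ties that margin to an analysis or decision rule; the stated tests are of zero difference

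*Combined protocol and SAP*

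**What the plan says.** Section 4a (Design) sets the frame: "This equivalence study will use an experimental design with randomization of parents". Objective 1 in Section 2 reads: "It is hypothesized that CPP will be equally as effective as PCIT for reducing child behavior problems based on parent report and observation". Objective 2 makes the same kind of claim for discipline, self-efficacy and observed parenting.

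Section 7c bases the sample size on the CBCL. Its null is that "the absolute difference in the post intervention means between the CPP and PCIT groups will be > 0.5 standard deviations", which it equates with more than 5 points; the alternative is a difference of at most 0.5 SD. It adds "We will use the more conservative two-sided test" and gives 99% power with 150 per arm, "using a two-sample comparison of means with alpha=0.05".

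The next paragraph of Section 7c is the analysis plan: "Hypothesis testing will mainly be conducted using repeated-measures MANOVA". Then: "Should the MANOVA be significant, univariate ANOVA will follow to identify the source of those differences". Testing is two-tailed at 0.05.

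Section 4b has "three assessment phases: baseline, 4 months post-baseline, and 9 months post-baseline", and Table 1 lists both an Externalizing and an Internalizing CBCL scale. The margin is not assigned to either scale or to either follow-up visit.

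**The concern.** An equivalence null is rejected when the data show that the difference is small enough. MANOVA and ANOVA, as normally run, reject when the data show that the difference is not zero. A significant result does not show a difference beyond 5 points, and a non-significant one is not in itself evidence of a difference below 5 points. The plan gives the second kind of test for a hypothesis of the first kind, and does not say how a non-significant MANOVA would be read.

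Equivalence on child behavior is objective 1, and objective 4 builds on it (comparable effects at less cost). Without a rule, two analysts could follow the plan on the same data and reach different conclusions, and the criterion could be chosen after the results are known.

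**Working it through.** **Inputs.** From Section 7c: 150 per arm, margin 0.5 SD = 5 points (so SD = 5/0.5 = 10), two-sided alpha 0.05. Assumed: equal arms, no baseline adjustment, no clustering, one post-intervention comparison.

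**1. The plan's own figure.** SE = 10 × √(2/150) = 1.155 points. Power to detect 5 points = Φ(5/1.155 − 1.960) = Φ(2.370) = 99.1%. The stated 99% reproduces. Two one-sided tests at zero true difference give 2Φ(4.330 − 1.645) − 1 = 99.3% (90% CI) or 2Φ(4.330 − 1.960) − 1 = 98.2% (95% CI). The stated power therefore cannot show which test was intended.

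**2. Where the two criteria part (t-based).**
- Significant if |difference| > 1.968 × 1.155 = 2.27 points.
- 90% CI inside ±5 if |difference| < 5 − 1.650 × 1.155 = 3.09 points.
- 95% CI inside ±5 if |difference| < 5 − 1.968 × 1.155 = 2.73 points.

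Between 2.27 and 3.09 (or 2.73) points the comparison is significant and the interval is also inside the margin. At a true difference of 2 points this happens in 24% of trials (90% CI) or 14% (95% CI).

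**3. The other direction.** At 150 per arm a non-significant simple comparison (at most 2.27 points) always has its CI inside ±5. The thresholds meet as numbers fall:

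| Per arm | Loss from 150 | Significant above | CI inside ±5 below |
|---|---|---|---|
| 105 | 30% | 2.721 | 2.720 (90% CI) |
| 124 | 17% | 2.501 | 2.499 (95% CI) |

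Below these numbers, non-significance no longer implies equivalence.

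**4. The multivariate gate.** The documents do not list the MANOVA outcomes. As a stand-in, take Hotelling's T² at one visit with p outcomes, equal correlation ρ, 150 per arm, and only the CBCL differing, by d = 0.5 SD. The noncentrality is λ = (150/2) × d² × [1 + (p − 2)ρ] / {(1 − ρ)[1 + (p − 1)ρ]}. The chance of a non-significant gate is the noncentral F probability below the 5% critical value, on p and 299 − p degrees of freedom:

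| p | ρ = 0 | ρ = 0.3 | ρ = 0.5 |
|---|---|---|---|
| 3 | 3.6% | 1.7% | 0.3% |
| 8 | 11.6% | 4.3% | 0.6% |
| 12 | 17.9% | 6.9% | 1.2% |

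In those trials no univariate CBCL test would follow, although the true difference sits at the margin.

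**5. Power of a margin-based rule.** At a true 0.2 SD and 150 per arm: Φ(0.3/0.1155 − 1.645) = 83% (90% CI) or Φ(0.3/0.1155 − 1.960) = 74% (95% CI). With an assumed 20% loss (120 per arm): 97% or 94% at zero difference, and 75% or 64% at 0.2 SD. With an assumed ICC of 0.05 and 9 parents per CPP group, SE = √[(1 + 8 × 0.05)/150 + 1/150] = 0.1265 SD, giving 77% or 66% at 0.2 SD.

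**The case against.** Four points deserve weight.

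- **The text leaves room for another test.** The sentence on the two-sided test directly follows the equivalence hypotheses, in a subsection that covers both sample size and statistical plan, and the MANOVA is only the main method. A reader might infer that the margin was meant for sizing alone. The documents do not settle that. What stands is narrower: the nearby phrases sit in the power statement, and neither says what result would show equivalence.
- **Section 7c glosses equal effectiveness as outcomes that differ neither clinically nor statistically.** Taken as a rule, this requires non-significance as well as a difference inside the margin, and the 24% or 14% overlap would then be an intended failure to show equivalence. But the phrase describes the aim of the sizing, and no analysis step applies it. The overlap is an error only if equivalence is judged by the margin alone.
- **The simple case does little harm with full data.** At 150 per arm and a true 5-point difference, a simple comparison is non-significant in only 0.9% of trials. The documents state no allowance for loss, so the crossovers at 105 and 124 per arm are a warning and not a forecast.
- **The gate's effect depends on an unstated outcome set.** One MANOVA per objective, with perhaps 3 outcomes, is as compatible with the text as one with 8 to 12. A reader might infer from the 18% figure that the gate often hides a difference at the margin. That needs many uncorrelated outcomes; with 3 the figure stays below 4%.

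**Conclusion.** The point holds as a mismatch between hypothesis and analysis: an equivalence null is posited, the stated tests are of zero difference, and no rule links the data to the margin. It should be fixed before analysis, because the trial's central claim depends on it.

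This does not rest on the illustrations. Their size rests on SD 10, 150 analysed per arm, no clustering and, for the gate, an assumed outcome set in which only the CBCL differs. With that gate, a true 5-point difference is missed in about 0.3% to 4% of trials with 3 outcomes and 0.6% to 18% with 8 to 12.

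A reader might also infer that the sample size is wrong. The documents do not support that: the stated power reproduces, and is almost the same for an equivalence test at zero true difference. Nor is the difference test misplaced throughout; it suits objective 3, where CPP is hypothesized to be better.

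**What to change.** - Make the primary CBCL analysis an estimate of the CPP minus PCIT difference for one named CBCL score at one named visit, not gated by the MANOVA. In choosing the visit, note that Section 4b says PCIT usually runs 6–8 months and CPP 3, so the 4-month visit falls during PCIT.
- Conclude equivalence only if the pre-specified CI lies wholly within ±5 points. State whether it is 90% (two one-sided tests at 0.05) or 95%, and whether statistical non-significance is also required.
- State that a non-significant MANOVA is not evidence of equivalence.
- For the other outcomes with an equivalence or no-difference hypothesis (objectives 1, 2 and 5), pre-specify a margin or report estimates with CIs and claim no equivalence.
- Keep difference tests for objective 3.

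**Cost.** No new data, only decisions taken before analysis. At 150 per arm the rule is well powered if the true difference is near zero. At 0.2 SD power is 83% (90% CI) or 74% (95% CI), and dropout or clustering by CPP group lowers it further, so the team should state the power it accepts under realistic loss.
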